1.1 Background Information and Study Rationale

1.1.1 Background Information

Atopic dermatitis (AD) (also called atopic eczema) is an intensely pruritic, chronic, relapsing, inflammatory skin disease [Bieber, 2008]. The characteristic signs and symptoms of AD include sensations of pruritis and burning, xerosis, erythematous papules and plaques, exudation, crusting, and lichenification. Quality of life is affected through sleep deprivation due to the intense and constant itching, as well as the stigma associated with having a visible skin disease [Carroll, 2005; Lewis-Jones, 2006]. Up to 30% of children may be affected by AD at some point, and 2% to 10% of adults have AD [Bieber, 2008]. Currently there is no curative therapy. Stabilizing the disease and reducing the number and severity of flares are the primary goals of treatment. Topical treatments directed at skin inflammation are a key factor in disease management, as is symptomatic relief of itching. Although multiple topical treatment options are available, there still remains a need for a topical treatment that combines a high level of efficacy with an acceptable safety profile that permits application to a large body surface area (BSA) without restrictions on duration of treatment.

Tapinarof (DMVT-505), formerly known as GSK2894512 and WBI-1001, is a fully synthetic naturally derived stilbene that is being developed by Dermavant Sciences, Inc. (Dermavant) as a novel anti-inflammatory agent for the topical treatment of AD and plaque psoriasis. The compound (number WBI-1001) was initially developed by Welichem Biotech Inc. (Welichem; Burnaby, British Columbia, Canada) and then was acquired by GlaxoSmithKline (GSK) on 31 July 2012 for further development in the rest of the world except China. Dermavant acquired the drug from GSK on 20 August 2018 for continued development. Development of tapinarof cream in Japan is being jointly pursued with Japan Tobacco Inc. (JT), with a Phase 3 program in PSO and AD scheduled to commence in late 2021. In China, the compound was independently developed by Beijing Wenfeng Tianji Pharmaceutical Technology Co. (BWTP) (Shenzhen Celestial) under the name benvitimod (active ingredient corresponds to tapinarof). BWTP was granted authorization to market benvitimod cream (a different formulation and excipient profile compared to tapinarof cream) as Symbiox® in China in July 2019.

Tapinarof cream, 1% is a white to off-white, oil-in-water emulsion intended for topical application to AD and psoriatic skin lesions, which has a novel mechanism of action. Tapinarof is a nonsteroidal, small molecule therapeutic aryl hydrocarbon receptor (AhR) modulating agent (TAMA) which exerts its therapeutic effects via agonism of AhR, a cytosolic ligand dependent transcription factor. Upon ligand binding, AhR translocates to the nucleus and dimerizes with AhR nuclear translocator (ARNT) forming an AhR ARNT heterodimer [Smith, 2017]. The AhR-ARNT heterodimer modulates gene transcription through direct and indirect interaction with DNA. By activation of this AhR signaling pathway, tapinarof has the potential to downregulate the expression of pro-inflammatory cytokines, including interleukin (IL)-4, IL-5, IL-6, IL-13, IL-17A and F, and eotaxin, and upregulate the expression of several skin barrier proteins, including filaggrin, hornerin, and involucrin. In addition, AhR also activates the antioxidative transcription factor nuclear factor-erythroid 2-related factor-2 (Nrf2), upregulating the expression of antioxidative enzymes [Smith, 2017; Furue 2019]. By targeting AhR, tapinarof has a biological profile that differs from that of currently available products, offering patients a truly novel therapeutic treatment option.

Two Phase 2b, 12-week, randomized, double-blind, vehicle-controlled, 6-arm, parallel group, dose-finding studies with topically applied tapinarof cream were conducted by GSK; 1 study each in subjects with AD or psoriasis. These 2 studies evaluated the safety and efficacy of tapinarof cream (Formulation F) at 2 concentrations (0.5% or 1% weight/weight [w/w]) and 2 application frequencies (once daily [QD] or twice daily [BID]) in 247 adult and adolescent subjects with AD and in 227 adult subjects with plaque psoriasis. In both studies, tapinarof showed a clear therapeutic effect compared with vehicle, with the 1% w/w concentration treatment groups demonstrating a higher proportion of subjects with treatment success compared with the 0.5% w/w concentration groups (applied QD and BID in the AD study). In both indications, the tapinarof 1% dosing groups showed a faster onset of action than the 0.5% dosing groups, and QD application had similar efficacy to BID application. In both Phase 2b studies, tapinarof showed an acceptable safety profile. Treatment-emergent adverse events (TEAEs) were reported with a higher frequency in the tapinarof groups than in the vehicle groups. The most frequent TEAEs ($\geq 5\%$ in any arm or in total) were nasopharyngitis, folliculitis, dermatitis contact, atopic dermatitis, upper respiratory tract infection, headache, vomiting, acne, application site dermatitis, miliaria, dermatitis allergic, and impetigo. The majority of TEAEs were mild or moderate in severity. In each study, the tapinarof 1% QD treatment group had a lower frequency of TEAEs than the tapinarof 1% BID treatment group.

Tapinarof has been evaluated in two identical Phase 3, 12-week, randomized, double-blind, vehicle-controlled trials in adult subjects with plaque psoriasis. These studies evaluated the safety and efficacy of tapinarof cream, 1% once a day versus vehicle cream once a day in a combined 1025 subjects randomized 2:1 tapinarof to vehicle. In both trials, tapinarof demonstrated superiority against vehicle on the primary endpoint, a Physician Global Assessment (PGA) score of 0 (clear) or 1 (almost clear) with a 2-point improvement at Week 12. In addition, tapinarof was highly statistically significant compared to vehicle on all secondary endpoints which included proportion of subjects achieving a 75% improvement in the Psoriasis Area and Severity Index, a PGA score of 0 or 1, change in percent body surface area (%BSA), and proportion of subjects achieving a 90% improvement in PASI at Week 12. TEAEs were reported with a higher frequency in the tapinarof group than in the vehicle group. The most frequent TEAEs ($\geq 5\%$ in any arm or in total) were folliculitis, nasopharyngitis, and contact dermatitis. The majority of TEAEs were mild or moderate in severity. In addition, a 40-week open label extension study was conducted which confirmed the safety profile observed in 12-week studies with no new safety signals emerging.

1.1.2 Study Rationale

This Phase 2a maximal use study is being conducted as part of a clinical development program to evaluate the safety and systemic exposure of tapinarof cream, 1% for the topical treatment of AD in subjects ages 2 to 17 years. Maximal use trials enroll subjects with the disease under study and who generally have more severe disease or with a large BSA of affected skin who might be more susceptible to systemic AEs. The purpose of these studies is to evaluate systemic exposure under conditions that would maximize the potential for drug absorption with the intended use of the product [Bashaw, 2014]. The results of this study are intended to support product registration in the United States and Canada.

1.2 Rationale for Study Design and Dose

The dose of tapinarof in this trial will be the 1% cream administered QD, the same as that studied in the Phase 3 pivotal trials in plaque psoriasis and in the maximal use study in plaque psoriasis. This is also the dose that

was selected for the Phase 3 pivotal trials in AD based on the efficacy and safety data from Study 203121 [Peppers, 2019]. In study 203121, applications of tapinarof cream at concentrations of 0.5% and 1% applied once or QD were evaluated. The groups treated with a 1% concentration showed higher efficacy and resulted in a quicker onset of effect than did the groups treated with a 0.5% concentration. Efficacy responses began as early as Week 2 and continued through Week 12. The proportion of subjects with $\geq 75\%$ improvement in Eczema Area Severity Index (EASI) was also higher for the 1% BID (60%) and 1% QD (51%) compared to vehicle (25-26%). Overall, both concentrations demonstrated an acceptable safety profile when applied once or BID with the 1% QD arm having a lower number of reported TEAEs compared to the 1% BID arm (54% vs 70%, respectively). QD application was selected as efficacy was similar between 1% BID and 1% QD regimens and provided a better safety profile. In addition, QD application may improve treatment adherence compared with more frequent dosing administrations.

Extrapolation of tapinarof safety, efficacy, and dosing regimen from adults to adolescents, and to children is appropriate on the grounds of similarity of skin development, pharmacokinetics (PK), formulation composition, and clinical endpoints. The tapinarof cream formulation does not contain excipients that would preclude its use in pediatric patients. Furthermore, the skin of infants would be expected to have similar barrier function to adults. Infants born at 30 and 32 weeks gestational age were found to have a fully functional stratum corneum comparable with that of adults [Kalia, 1998]. Another study demonstrated that the way the stratum corneum stores and transports water becomes adult-like after the first year of life [Nikolovski, 2008]. In GSK study 203121, the safety, efficacy, and plasma concentrations of tapinarof were similar between adults and adolescents. Therefore, there is no evidence to suggest that safety, efficacy, or dosing regimen in the pediatric population down to age 2 will be different from that in adults. Thus, product strength and dosing frequency is the same for all subjects in the study, regardless of age.

An open-label study is appropriate as the main objective of a maximal use study is to assess pharmacokinetics and safety. Since systemic absorption is likely to be greatest early in the study when the skin has the most lesions, short-term treatment is adequate to assess the study objectives. This study includes an open label treatment phase in which subjects will receive tapinarof cream, 1% QD for 27 days. Tapinarof has a unique PK profile whereby the highest plasma concentrations are observed in the first week of the treatment period followed by a subsequent decline to undetectable or near undetectable levels after multiple weeks of dosing. Accumulation of drug after multiple dosing has not been observed in any clinical study with tapinarof to date. The 27-day treatment phase was selected to ensure steady state is achieved and to provide a treatment duration that allows for evaluation of safety in this population with extensive disease that has not been evaluated to date.

1.3 Potential Risks and Benefits

To assess any potential impact on subject eligibility with regard to safety, the Investigator must refer to the current version of the tapinarof Investigator's Brochure for detailed information regarding warnings, precautions, contraindications, adverse events (AEs), and other significant data pertaining to the study drug being used in this study.

1.3.2 Benefit Assessment

Subjects may experience improvements in their AD during the course of the study and may benefit from the additional safety assessments conducted as part of the study (e.g., physical examination, laboratory tests). Subjects in the study will also contribute to the process of developing a novel anti-inflammatory agent for the topical treatment of AD. Furthermore, subjects participating in this trial will be offered enrollment in a long-term safety study (DMVT-505-3103), if eligibility requirements are met, where they will have continued access to tapinarof for an additional 48 weeks.

1.3.3 Overall Benefit Risk

Taking into account the measures taken to minimize risk to subjects in this study, the potential risks identified in association with tapinarof are justified by the anticipated benefits that may be afforded to subjects with AD.

2 Objectives and Endpoints

The objectives and associated endpoints of the study are as follows:

Objectives	Associated Endpoint
Primary	

To evaluate the safety and tolerability of tapinarof cream, 1% QD in pediatric subjects ages 2 to 17 years old with extensive ADTo evaluate the PK of tapinarof cream, 1% QD in pediatric subjects ages 2 to 17 years old with extensive AD	
Incidence, frequency and duration of TEAEs and serious adverse events (SAEs)Change from Baseline in laboratory valuesChange from Baseline in vital signsMean Investigator-assessed local tolerability scores (LTS) scores by visit (overall and sensitive areas)Tapinarof plasma PK parameters on Day 1, if data permit, including:
area under the plasma concentration versus time curve from time 0 to the last quantifiable concentration (AUC_{0-last})maximum plasma concentration (C_{max})time to maximum plasma concentration (t_{max})time of last quantifiable concentration (t_{last})Tapinarof plasma concentration on Day 28
Secondary	Secondary: 
To assess the efficacy of tapinarof cream, 1% QD in pediatric subjects ages 2 to 17 years old with extensive AD
	
Change in Validated Investigator Global Assessment in Atopic Dermatitis (vIGA-ADTM) score from Baseline at each study visitProportion of subjects who have a vIGA-ADTM score of clear or almost clear (0 or 1) at each study visitProportion of subjects with $\geq 50\%$ improvement in EASI score from Baseline at each study visitProportion of subjects with $\geq 75\%$ improvement in EASI score from Baseline at each study visitProportion of subjects with $\geq 90\%$ improvement in EASI score from Baseline at each study visitMean change and percent change in EASI score from Baseline at each study visitMean change and percent change in %BSA affected from Baseline at each study visitMean change and percent change in BSA x vIGA-ADTM values from Baseline at each study visitProportion of subjects with a Baseline PP-NRS score ≥ 4 who achieve ≥ 4-point reduction in the PP NRS from Baseline at each study visitProportion of subjects ≥ 12 years old with a Baseline PP-NRS score ≥ 4 who achieve a ≥ 4-point reduction in PP-NRS score from Baseline at each study visitProportion of subjects 2 to < 12 years old with a Baseline PP-NRS score ≥ 4 who achieve a ≥ 4-point reduction in PP-NRS score from Baseline at each study visitMean change in PP-NRS score from Baseline to Day 28 by age group

3 Study Design

3.1 Overall Design

This is a Phase 2a, multicenter, open-label, safety, tolerability and PK study in pediatric subjects with AD. The study will consist of three phases: Screening (up to 30 days), Treatment (27 days), and Follow-up (approximately 7 days).

At Day 1 (Baseline), eligible subjects and/or their caregiver(s) will be instructed on how to apply tapinarof cream, 1% while under the supervision of site personnel in the clinic and have collection of PK samples to assess systemic absorption. During the treatment period, subjects and/or their caregiver(s) will apply tapinarof cream, 1% to affected areas once a day for 27 days, including newly appearing lesions and lesions/areas that improve during the study. Subjects or caregivers will apply sufficient study drug to cover completely each lesion with a thin layer of study drug and will record the time of study drug application and daily itch score (Peak Pruritus-Numeric Rating Scale [PP-NRS]) in a daily diary provided by the study site. (Note that subjects are allowed, but not required, to treat scalp lesions with study drug; however, efficacy analyses will not include assessment of AD in this area.) Subjects will return to the clinic on Days 8 and 28 for study assessments. On clinic visit days, subjects and/or their caregiver(s) will apply study drug under the supervision of site personnel and instructed/reminded on how to apply study drug (except during the final treatment/end-of-study visits). Additionally, subjects will be contacted by phone at Day 15 to assess AEs and concomitant medications, to review study drug administration instructions, confirm subject's continued participation in this study, and reminded to complete their daily diary and bring it with them to the next clinic visit.

Study drug will be dispensed and applied to subjects during the clinic visits and will be administered at home between clinic visits as instructed by site personnel. Subjects and/or caregivers will be advised to maintain the approximate dosing time chosen at the beginning of the study for their full study participation.

Nonmedicated emollients that do not contain salicylic acid may be used on nonlesional skin; emollients should not be applied to lesional skin during treatment. The same emollient should be used throughout the subject's participation in the study.

Study drug application instructions will be reviewed at all post-baseline clinic visits and during the planned study phone call. The time of the dose application and assessments will depend on the time of the clinic visit. Therefore, the timing of the clinic visit may lead to a change in the subject's chosen dosing time for that day.

On Day 28 of this study, a final PK sample will be collected and subjects will have the option to enroll in a separate open-label long-term safety study for an additional 48 weeks. Subjects who choose not to participate in the open-label long-term safety study or who fail to qualify for participation in the open-label long-term safety study will complete a Follow-up Visit (Day 35) approximately 7 days after the end of treatment in this study. Subjects who withdraw from the study before Day 28 will complete an Early Termination Visit as their final visit and are not eligible for the open-label long-term study. Subjects that complete an Early Termination visit will not complete a Follow-up visit.

Study duration for subjects who complete this study and who fail to qualify for participation in the open-label long-term safety study, or who qualify to participate in the open-label long-term safety study but elect not to enroll in that study is approximately 9 weeks in total. Study duration for subjects who complete this study

and are eligible and decide to participate in the open-label long-term safety study is approximately 8 weeks in total.

Efficacy assessments will include v-IGA-AD™ score, %BSA affected, EASI, and PP-NRS. Safety assessments will include AEs, clinical laboratory tests, physical examination, vital signs, and LTS.

Pharmacokinetics will be assessed at Days 1 and 28. The screening blood sample will be used for baseline PK if the subject is enrolled. Blood samples for PK should not be collected from any anatomic site where study drug has been applied in order to minimize potential contamination.

Refer to Section 6 for descriptions of study procedures and assessments and Section 7 and the Schedule of Assessments ([Table 1](#)) for timing of procedures and assessments

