4.2 Inclusion Criteria

Each subject must meet all of the following criteria to be eligible to participate in the study:

1. Male and female subjects ages 2 to 17 years with a clinical diagnosis of AD by Hanifin and Rajka criteria [[Hanifin, 1980](#)] (see [Appendix 1](#)).
2. Subjects with AD covering $\geq 25\%$ of the BSA for subjects ages 12-17 years old, or $\geq 35\%$ of the BSA for subjects ages 2-11 years old, suitable for topical therapy. Scalp should be excluded from the BSA calculation to determine eligibility during Screening and at Baseline, and for all efficacy assessments.
3. A vIGA-AD™ score of 3 or greater at Screening and Baseline (pre-dosing).
4. AD present for at least 6 months for subjects ages 6-17 years old or 3 months for subjects ages 2 to 5 years old, confirmed by prior medical documentation and/or according to the subject and/or caregiver(s).
5. Female subjects of childbearing potential who are engaging in sexual activity that could lead to pregnancy should use one of the following acceptable birth control methods while on study and for 4 weeks after the last exposure to study drug.
 - Acceptable contraception methods include intrauterine device, hormonal contraceptives, barrier method (e.g., condom or diaphragm), or surgical sterilization of male partner (vasectomy)
 - Subjects who claim abstinence as their method of contraception are allowed provided they agree to use a barrier method (e.g., condom or diaphragm) should they become sexually active from Screening to 4 weeks after the last dose of study drug
 - Non-child-bearing potential is defined as:
 - premenarchal
 - pre-menopausal females with a documented bilateral tubal ligation, bilateral oophorectomy, hysterectomy, or hysteroscopic sterilization
6. Female subjects of childbearing potential must have a negative serum pregnancy test at Screening and a negative urine pregnancy test at Baseline (Day 1).
7. Subject, subject's parent(s), or legal representative must be capable of giving written informed consent, which includes compliance with the requirements and restrictions listed in the consent/assent form; written informed consent must be obtained prior to any study related procedures.

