4.6.1 Reasons for Withdrawal from the Study

Study drug will be discontinued and the subject will be withdrawn from the study for any of the following reasons:

- Subject has an AE that is considered to be related to study drug or procedures AND is severe enough to warrant treatment discontinuation, as determined by the Investigator (Section 8.1).
- Pregnancy
- Any Grade 3 or 4 AE, based on National Cancer Institute Common Terminology Criteria for Adverse Events (CTCAE) criteria, considered causally related to study drug (Section 8.2.2)

Study drug may be discontinued and the subject withdrawn from the study for any of the following reasons:

- Subject requires concurrent prohibited medication during the study. Nonmedicated emollients that do not contain salicylic acid may be used on nonlesional skin; emollients should not be applied to lesional skin during treatment. The same emollient should be used throughout the subject's participation in the study.

NOTE: If, in the opinion of the Investigator and the study Medical Monitor, such medication will not interfere with the conduct or interpretation of the study or compromise the safety of the subject, then the subject may continue to receive study drug. If the subject is permanently discontinued from study drug, they may remain in the study for safety assessments as needed, at the discretion of the Investigator and Medical Monitor, but they are not eligible to enroll in the open-label, long-term safety study.

- Subject noncompliance

- Investigator noncompliance
- Discontinuation of the study at the request of the Sponsor, regulatory agency, or an Institutional Review Board (IRB)/Independent Ethics Committee (IEC).

If a subject meets a withdrawal criterion during treatment, an Early Termination visit will be required (Section 7.7).

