7.6 Visit 5; Follow-Up (Day 35 ±3 Days)

Subjects who do not enroll in the open-label long-term safety study will return to the study site 7-10 days after Day 28 to complete follow-up assessments as follows:

- Brief physical examination
- If needed, blood sample collection for clinical laboratory tests
- If needed, urinalysis
- Vital signs measurement
- AE recording
- Concomitant medication recording
- vIGA-AD™ score (excluding subject's scalp)
- %BSA affected calculation (excluding subject's scalp)
- EASI (excluding subject's scalp)

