8.1 Adverse Events, Serious Adverse Events, and Adverse Events of Special Interest

The Investigator or site staff is responsible for detecting, documenting, and reporting events that meet the definition of an AE, SAE, or adverse events of special interest (AESIs). At each visit/contact, subjects should be questioned in a general way so as not to introduce bias in detecting AEs and/or SAEs. Open-ended and non-leading verbal questioning of the subject is the preferred method to inquire about AE occurrence.

Investigators are not obligated to actively seek AEs or SAEs in former study subjects. However, if the Investigator learns of any SAE, including a death, at any time after a subject has been discharged from the study, and he/she considers the event reasonably related to the study drug or study participation, the Investigator should promptly notify the Sponsor.

A narrative will be written and included in the Clinical Study Report for all SAEs and AESIs, and for all AEs that lead to study discontinuation.

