8.3 Time Period and Frequency for Event Assessment and Follow-Up

8.3.1 Adverse Event Reporting

All AEs will be collected from the time of signed informed consent until the final visit.

Any AEs assessed as related to study participation (e.g., protocol-mandated procedures, invasive tests, or change in existing therapy) will be collected from the time a subject consented to participate in the study up to and including any follow-up contact.

All SAEs will be recorded in the CRF and reported to the Sponsor within 24 hours via email or phone (refer to the [Medical Monitor / Sponsor Information Page](#) for contact information) (see Section [8.4](#)).

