8.5 Pregnancy Management and Reporting

Any female subject who becomes pregnant during the study will be withdrawn. Details will be collected for all pregnancies in female subjects and female partners of male subjects that begin after the start of dosing and through the Follow-up visit. Pregnancy is not automatically considered an AE.

If a pregnancy is reported, then the Investigator should complete a Pregnancy Report Form and submit via email or fax to the Pregnancy Reporting Contact for which contact information can be found on the [Medical Monitor / Sponsor Information Page](#) of this protocol, within 2 weeks of learning of the pregnancy. The subject will also be followed to determine the outcome of the pregnancy. Information on the status of the mother and child will be forwarded to the Sponsor. Generally, follow-up will be no longer than 6 to 8 weeks following the estimated delivery date. Any premature termination of the pregnancy will be reported.

Any SAE occurring in association with a pregnancy brought to the Investigator's attention after the subject has completed the study and considered by the Investigator as possibly related to the study drug must be promptly reported to the Sponsor or the Sponsor's representative.

The Investigator must attempt to collect pregnancy information on any female partners of male study subjects who become pregnant while the subject is enrolled in the study. Pregnancy information must be reported to the Sponsor or the Sponsor's representative as described above. The partner will also be followed to determine the outcome of the pregnancy. Information on the status of the mother and child will be forwarded to Sponsor or the Sponsor's representative. Generally, follow-up will be no longer than 6 to 8 weeks following the estimated delivery date. Any premature termination of the pregnancy will be reported on the Pregnancy Report Form.

9 Data Management

For this study, subject data will be entered into the Sponsor-defined CRFs, transmitted electronically to the Sponsor or designee, and combined with data provided from other sources in a validated data system.

Management of clinical data will be performed in accordance with applicable Sponsor standards and data cleaning procedures will be used to ensure the integrity of the data, e.g., errors will be corrected, and inconsistencies queried in the data.

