10.2 Determination of Sample Size

There is no formal statistical hypothesis planned and the sample size is mainly based on feasibility and an estimated number of subjects needed to address the objectives of the study.

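### After an Early Termination visit no contact is scheduled to collect new adverse events, and pregnancy collection ends about 20 days before the 4-week contraception period, with no defined end for early terminators

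*Protocol*

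**What the plan says.** **End of adverse event collection.** Protocol section 8.3.1: "All AEs will be collected from the time of signed informed consent until the final visit". Section 6.3.1 words the same limit as the final visit or contact. Section 8.1 adds: "Investigators are not obligated to actively seek AEs or SAEs in former study subjects". Related SAEs that the investigator happens to learn of after discharge are still reportable.

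**Early termination.** Section 4.6.1: "If a subject meets a withdrawal criterion during treatment, an Early Termination visit will be required". Section 3.1 makes that the final visit: "Subjects that complete an Early Termination visit will not complete a Follow-up visit". Sections 4.6.1, 4.6.2 and 7.7 set no minimum interval between the last dose and this visit.

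**Open events.** Section 8.3.2 follows every reported event, serious or not, until it resolves, stabilizes, is explained or the subject is lost. Sections 8.2.1.2.2 and 8.2.1.2.3 require weekly follow-up of Grade 3 and Grade 4 events that permanently stop the drug. Table 1 has no column for this.

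**Pregnancy.** Inclusion criterion 5 (section 4.2) requires contraception "while on study and for 4 weeks after the last exposure to study drug". Section 8.5 collects pregnancies "that begin after the start of dosing and through the Follow-up visit". Urine tests are listed at Day 28 and Early Termination (sections 7.5, 7.7), and none at Follow-up (section 7.6).

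**Follow-up timing.** The heading of section 7.6 gives Day 35 ±3. Its text has non-rollover subjects "return to the study site 7-10 days after Day 28 to complete follow-up assessments as follows".

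**The concern.** Incidence, frequency and duration of TEAEs and SAEs are primary endpoints, in a pediatric study meant to support registration. A completer who does not roll over gets a visit about a week off drug at which new events are asked about. A child who terminates early gets whatever time happens to separate the last dose from the Early Termination visit, possibly none. If that child has no open event, nothing later is scheduled. A new event after that point enters the data only if the family reports it or the investigator learns of a related SAE.

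For pregnancy, the protocol asks for contraception for 4 weeks after last exposure but stops collecting pregnancies much earlier. For early terminators the stated end point is a visit that they do not have. A pregnancy beginning in the uncovered weeks need not be reported under section 8.5, and no scheduled test could find it.

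**Working it through.** There is no power calculation to reproduce (section 10.2: "There is no formal statistical hypothesis planned and the sample size is mainly based on feasibility"). The check is date arithmetic and a comparison of passages.

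**Inputs**
- Last dose: the day before the Day 28 visit, so nominally Day 27. Section 3.3 gives 27 intended doses for a visit exactly on Day 28, and neither Table 1 nor section 7.5 lists a dose at that visit.
- Alternative last dose: Day 28, because one sentence of the synopsis has 28 days of application. The synopsis elsewhere says 27, and the two must be reconciled.
- Visit windows: Day 28 ±2 and Day 35 ±3 (Table 1).
- Contraception period: 4 weeks = 28 days after last exposure.

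**The plan's own figures**
- Day 35 − Day 28 = 7 days, matching the stated interval of about 7 days.
- (30 + 27 + 7)/7 = 9.1 weeks and (30 + 27)/7 = 8.1 weeks, matching the stated durations of about 9 and 8 weeks.

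**Off-drug adverse event collection, completers not rolling over**
- Nominal: 35 − 27 = 8 days. Last dose on Day 28: 35 − 28 = 7 days.
- Extremes: a Day 28 visit on Days 26–30 puts the last dose on Days 25–29, and Follow-up is on Days 32–38. Minimum 32 − 29 = 3 days; maximum 38 − 25 = 13 days.
- Using the text of section 7.6, with the visit on Day 28: 7 + 1 = 8 to 10 + 1 = 11 days.

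**Off-drug collection, early terminators**
- No open event: from the last dose to the Early Termination visit, with no stated minimum, so 0 days is possible.
- Open event: until that event resolves or stabilizes. Section 8.1 requires open-ended questioning at each contact, so new events can be picked up while this lasts. But section 3.1 calls the Early Termination visit final, and the weekly contacts appear nowhere in the schedule.

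**Pregnancy, completers not rolling over**

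| Last dose to Follow-up | Days of 28 not covered |
|---|---|
| 8 days (last dose Day 27; period ends Day 55) | 28 − 8 = 20 (71%) |
| 7 days (last dose Day 28; period ends Day 56) | 28 − 7 = 21 (75%) |
| 13 days (longest) | 28 − 13 = 15 (54%) |
| 3 days (shortest) | 28 − 3 = 25 (89%) |

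For early terminators the end of the period cannot be computed, because there is no Follow-up visit.

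**Section 7.6.** Day 35 ±3 is Days 32–38, which is 32 − 28 = 4 to 38 − 28 = 10 days after Day 28. The text allows 7 to 10. A Day 32 visit satisfies the heading and breaks the text.

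**Weight of one missed case.** With about 12 children per cohort and 36 overall, one child whose only event is missed moves incidence by 1/12 = 8.3 points in a cohort and 1/36 = 2.8 points overall.

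**Does the SAP repair this?** No. SAP section 13.2 includes all reported events for subjects not rolling over, so the analysis imposes no early cut-off; the gap is in collection. The same section defines the last study visit, used to impute event end dates, for rollover and Follow-up subjects only.

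**The case against.** A reader might infer that children withdrawn for toxicity go unobserved off drug, or that new events are missed mainly in those stopped for harm. The documents do not support this. A Grade 3 or 4 event that permanently stops the drug brings weekly follow-up. Every open event is followed to resolution or stability, and each contact includes general questioning. Section 8.2.2 records drug- or participation-related events through any follow-up contact. Section 7.8 allows unscheduled visits, and a note in section 4.6.1 lets a subject permanently off drug stay for safety assessments at discretion. A child with an open severe event may be contacted more often than a completer. All of that stands, and it confines the gap to early terminators without an open event, or whose open event has closed.

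A reader might also infer that a pregnancy conceived during treatment is lost. Section 8.5 goes by when the pregnancy begins, so one that begins on treatment is in scope even if found later. Possibly related SAEs associated with a pregnancy also remain reportable after completion.

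Finally, the 28 days is a contraception rule, and no visible text says that pregnancy collection must match it. That is fair: reading it as a risk window is an inference. The amendment summary names a section 1.3.1.3 on reproductive toxicity that is not in the public text, so any rationale there cannot be weighed.

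None of this supplies a scheduled contact after Early Termination, an end date in section 8.5 for early terminators, or agreement within section 7.6.

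**Conclusion.** The point holds in three parts.

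1. New adverse events after Early Termination are not systematically collected in subjects with no open event. Their scheduled off-drug window can be 0 days, against nominally 8 (or 7) for completers who do not roll over. The weekly follow-up of Grade 3 and 4 events must be reconciled with the Early Termination visit being final.
2. Pregnancy collection for completers who do not roll over ends nominally 20 days (or 21) before the contraception period does, and it has no defined end for early terminators.
3. Section 7.6 contradicts itself on when Follow-up takes place.

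The nominal figures assume visits on their target days. The 3-to-13-day range pairs opposite ends of the visit windows and is an outer bound. The plan does not project the number of early terminators. The pregnancy gap concerns a few subjects: those of child-bearing potential, mostly within a cohort of about 12 adolescents, who do not roll over. For rollover subjects observation here ends about a day after the last dose (28 − 27 = 1) and continues in a study whose protocol is not available, so nothing is concluded about them. The gap touches a primary safety endpoint and is cheap to close, so it merits an amendment.

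**What to change.** The changes concern data collection only.

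- **Sections 3.1, 7.7, 8.3.1 and Table 1:** add one telephone contact for early terminators, covering adverse events, SAEs and concomitant medication, at the same interval after the last dose as the Follow-up visit. End their adverse event collection at the later of that contact and the last event follow-up contact. Give the weekly follow-up of section 8.2.1.2 a place in the schedule, and reconcile it with the statement that Early Termination is the final visit.
- **Section 8.5:** for all subjects not rolling over, including early terminators, collect pregnancies that begin through 4 weeks after the last application. Add one telephone contact at that time for subjects of child-bearing potential.
- **Section 7.6:** reconcile the two Follow-up windows into one. Reconcile 27 and 28 days of application in the synopsis as well, since the off-drug count depends on it.
- **SAP section 13.2:** extend the definition of the last study visit to early terminators.

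Telephone collection of adverse events and medication is already used at Day 15, so no new procedure is needed. The cost is amendment wording, one or two short calls for a few subjects, minor site time and a slightly later last contact.
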